#### **9.5. Blinding**

To maintain the study blind, all study drug kits will be packaged with blinded labels. Investigators will distribute the blinded study drug kits by kit number to patients as assigned by the IWRS. All patients, investigators, site personnel, and laboratories with direct involvement in the conduct of the study or their designees will be blinded to treatment assignments and appropriate measures will be taken to ensure the blind is maintained to reduce potential bias. Some Sponsor personnel may have access to treatment assignments during dose escalation (Part 1), but during Part 2, all Sponsor personnel will be blinded to treatment assignment.

The only people with access to treatment assignments for Part 2 will be those individuals who maintain the IWRS, the DSMB, the unblinded statistical team providing data to and analyzing data for the DSMB, and safety personnel without direct involvement in the conduct of the study who are assigned to report unblinded data to regulatory authorities as required.

The extension will be considered open-label. All patients in the extension will be assigned RTA 408 150 mg. Patients will not be unblinded to study treatment in Part 1 or Part 2 upon entering the extension study.

##### **9.5.1. Patient Unblinding**

Although there is no known antidote to RTA 408, under rare circumstances, unblinding may be considered medically necessary for safety reasons. Unless faced with a life-threatening medical situation, the investigator should contact the medical monitor to discuss if there is a medically compelling reason to unblind the patient's treatment assignment. After the discussion, the investigator may proceed to unblind the patient, as appropriate. If unblinding is required, the investigator will utilize the IWRS to perform the unblinding. If a study drug assignment is unblinded, a description of the event that required unblinding must be documented by the investigator in the patient's source documents. Patients must discontinue taking study drug if their treatment assignment has been unblinded to the investigator (or designee), but they should remain blinded and continue attending all study visits and should undergo all study assessments. Patient treatment assignments must not be unblinded in the case of an AE or SAE, except as described above.

### **9.5.2. Unblinding for Regulatory Submission**

In situations where a regulatory body requires unblinding and reporting of a particular SAE, the appropriate bodies (e.g., ethics committees, IRBs) must be provided with unblinded information according to the applicable regulatory requirement. This information must not be conveyed to the investigator, site personnel, or patient; therefore, this type of unblinding does not necessitate that the patient discontinue taking study drug.

## **9.6. Unscheduled Visits**

Unscheduled visits are allowed for the following reasons:

- Patient rescreening
- Management of an AE or SAE
- Performance of additional laboratory tests for clinically abnormal test values or to confirm a possible pregnancy
- If the investigator feels that it is clinically appropriate for patient safety

## **9.7. Pregnancy**

### **9.7.1. Women of Childbearing Potential**

Women of childbearing potential (WOCBP) are female patients who are not surgically sterile (no history of bilateral tubal ligation, hysterectomy, or bilateral salpingo-oophorectomy), do not have fallopian inserts with confirmed blockage, have not had reproductive potential terminated by radiation or chemotherapy, and are not postmenopausal for at least 1 year.

### **9.7.2. Methods of Birth Control**

From the Screening Visit, while taking study drug, and until 3 months after taking the final dose of study drug, WOCBP must agree to practice one of the following methods of birth control:

- Use of a double-barrier contraception method, defined as male use of a condom and female use of a barrier method (e.g., contraceptive sponge, spermicidal jelly or cream with or without a diaphragm)
- Use of hormonal contraceptives (oral, parenteral, vaginal, or transdermal) for at least 3 months prior to study drug administration
- Use of an intrauterine device
- Complete abstinence from sexual intercourse
- Male sterilization (with the appropriate post-vasectomy documentation of the absence of sperm in the ejaculate.) The vasectomized partner should be the sole partner for that subject.

From the Screening Visit, while taking study drug, and until 3 months after taking the final dose of study drug, males who have female partners of childbearing potential must agree to practice one of the following methods of birth control:

- Have had a vasectomy (at least 6 months earlier)
- Use of a double-barrier contraception method, defined as male use of a condom and female use of a barrier method (e.g., contraceptive sponge, spermicidal jelly or cream with or without a diaphragm)
- Partner use of hormonal contraceptives (oral, parenteral, vaginal, or transdermal) for at least 3 months prior to study drug administration
- Partner use of an intrauterine device
- Complete abstinence from sexual intercourse

Male patients must also agree to not donate sperm starting on the first day of treatment until approximately 3 months after last dose of study drug.

### **9.7.3. Suspected Pregnancy**

During the study, all WOCBP must be instructed to contact the investigator immediately if they suspect they might be pregnant (e.g., late or missed menstrual period). Male patients must be instructed to contact the investigator if a sexual partner suspects she may be pregnant.

If a patient or investigator suspects that the patient may be pregnant, the study drug must be withheld until the results of a serum pregnancy test are available. If pregnancy is confirmed with a serum pregnancy test, the patient must discontinue taking study drug but continue to attend all study visits and undergo all study assessments. The investigator must immediately report a pregnancy associated with study drug exposure and record the event.

Pregnancy is not considered an AE; however, the investigator must follow a pregnant patient or the pregnant female partner of a male patient (if consenting) and report follow-up information regarding the course of the pregnancy, including perinatal and neonatal outcome. Infants resulting from such pregnancies should be followed for a minimum of 8 weeks. The Sponsor or its designee may contact the investigator to request additional information throughout the course of the pregnancy.

The following pregnancy outcomes must be considered SAEs and will require additional reporting in the case report form (CRF) and on an SAE form:

- Congenital anomaly/birth defect
- Stillbirth
- Spontaneous miscarriage

### **9.8. Treatment Interruption**

In the case of serious toxicities, the investigator may choose to interrupt treatment with study drug. If study drug treatment interruption exceeds 21 total days, a protocol deviation should be noted. Dose reductions are not permitted. Patients who are permanently discontinued from study drug for any reason should still complete all Part 1 and Part 2 study visits and undergo all scheduled study assessments, if possible. If the toxicity has resolved such that the investigator does not consider continued drug treatment to be an additional risk to the patient, the investigator may restart study drug treatment. Patients who are permanently discontinued from study drug

during the extension should complete the end of study assessments, and be terminated from the study.

## **9.9. Study Procedures**

To avoid inter-observer variability, every effort should be made to ensure that the same individual who made the initial baseline determination completes all subsequent assessments. All assessments occur in the study center clinic with the exception of those assessments for lab collection at Screening (all patients, Part 1 and Part 2) and Visit 3 (Part 1 only), which may be performed by a home health visit nurse (at appropriate locations and approved by Sponsor) and those assessments for Visits 6 and 8 in Part 1 and Visits 3, 6, 10 and 12 in Part 2, which will be performed via telephone contact. During the extension every effort should be made to ensure patient assessments are performed on-site. If this is not possible, home health visits are acceptable. For more detail regarding use of home health services see [Appendix 13](#) (COVID-19 Mitigations).

### **9.9.1. Informed Consent**

Written informed consent (Section [17.3](#)) must be obtained from the patient before any study related procedures are performed, and if there is a change in the study procedures that could affect the patient's willingness to participate-. Patients have the option to separately consent to have video recorded during the 25-foot timed walk and 25-foot normal walk tests at selected sites.

### **9.9.2. Inclusion/Exclusion Criteria**

Inclusion and exclusion criteria should be reviewed at the times indicated in [Table 3](#), [Table 4](#), and [Table 5](#). Patients must meet all of the inclusion criteria and none of the exclusion criteria for entry into the study. Investigators and/or study site personnel should contact the medical monitor for any questions regarding patient eligibility.

### **9.9.3. Demographics and Baseline Disease Characteristics**

Demographic data, including sex, age, race, and ethnicity, and baseline disease characteristics, including, but not limited to, documentation of genetic confirmation of Friedreich's ataxia and presence or absence of pes cavus, will be collected at the time indicated in [Table 3](#) and [Table 4](#).

### **9.9.4. Pes Cavus Assessment**

The process for classifying pes cavus will be described in a separate study manual. Pes cavus will be assessed at the times indicated in [Table 4](#) and [Table 5](#). Patients who participated in Part 1 of the study must complete a pes cavus assessment at the Extension Study Screening visit ([Table 5](#)).

### **9.9.5. Foot X-Ray**

The foot x-ray assessment will be performed to quantify the foot structure of patients with and without pes cavus. Specific radiological angles of the foot will be quantified by a central reader. Radiological angles assessed from a lateral image of the foot may include but are not limited to: tibia-talar angle, talo-calcaneal angle, tibia-calcaneal angle, talo-first metatarsal angle,

calcaneal pitch angle, and naviculocuboid overlap. The x-ray of the lateral view of the right foot will be collected once per patient at the time indicated in [Table 4](#). Patients should complete the foot x-ray at Screening; however, if a patient was not able to complete the foot x-ray at Screening, it may be completed at any point during the first 52 weeks of the study.

#### **9.9.6. Prior and Concomitant Medications**

Information on prior and concomitant medications will be collected at the times indicated in [Table 3](#), [Table 4](#), and [Table 5](#). The name, dose, and frequency of all medications that the patient is taking or has taken within 30 days prior to Study Day 1 must be recorded during the study and until the final visit. All allowed and excluded medications should be recorded, including all prescription drugs, herbal products, vitamins, minerals, and over-the-counter medications. Trade or generic drug names should be used whenever possible.

#### **9.9.7. Medical History**

A complete medical history (e.g., per patient report) that includes all medical history within the past 5 years will be collected and recorded at the time indicated in [Table 3](#), [Table 4](#), and [Table 5](#).

#### **9.9.8. Height**

Height should be measured without footwear, head coverings, or prosthetics at the time indicated in [Table 3](#) and [Table 4](#).

#### **9.9.9. Echocardiogram**

An echocardiogram will be recorded at the times indicated in [Table 3](#), [Table 4](#), and [Table 5](#) after the patient has rested for approximately 10 minutes in a supine position. For patients with echocardiograms collected within 90 days prior to Screening Visit, the most recent echocardiogram can be used to assess cardiac function and patient eligibility. Patients are ineligible to participate in the study if they have pericardial constriction, restrictive or congestive cardiomyopathy, or left ventricular ejection fraction <40%. However, patients with mild to moderate cardiomyopathy associated with Friedreich's ataxia are not excluded.

Patients from Part 1 of the study that want to participate in the Extension must have an echocardiogram collected within 90 days prior to Extension Day 1.

#### **9.9.10. Electrocardiogram**

A 12-lead electrocardiogram (ECG) will be recorded at the times indicated in [Table 3](#) and [Table 4](#) after the patient has rested for approximately 10 minutes in a supine position. The heart rate from the ECG machine should not be used as part of the vital sign measurements.

An ECG is required for eligibility. If a patient has had an ECG completed within 90 days prior to the Screening Visit, the most recent ECG can be used as the screening assessment for patient eligibility.

#### **9.9.11. Vital Sign Measurements**

Vital sign measurements should be taken at the times indicated in [Table 3](#), [Table 4](#), and [Table 5](#) and include the patient's heart rate (beats/minute), blood pressure (mm Hg), and body

temperature (°C or °F). Blood pressure should be taken after the patient has rested in a sitting position for approximately 5 minutes. The same arm (usually the non-dominant arm) and the appropriate size cuff should be used for each measurement.

#### **9.9.12. Weight and Body Mass Index**

Weight should be measured at the times indicated in [Table 3](#), [Table 4](#), and [Table 5](#). BMI will be calculated within the eCRF each time the weight is recorded. If patients are weighed at the Screening Visit with additional leg braces, walkers, or shoes, all additional weight assessments must be conducted with the same appendages.

#### **9.9.13. Physical Examination**

A comprehensive physical examination must be performed by a physician, physician assistant, or registered nurse practitioner at the times indicated in [Table 3](#), [Table 4](#), and [Table 5](#). If possible, the same individual should perform each physical examination on a patient during the study. The examination must include the following organ or body system assessments: general appearance, head, eyes, ears, nose, throat, neck, musculoskeletal, cardiovascular, lymphatic, respiratory, abdomen, dermatologic, extremities, and neurological. Assessments of any specific signs or symptoms reported by the patient must also be performed and documented along with any other findings of note. Each body system finding must be assessed for clinical significance. Clinically significant findings at the Screening Visit must be included in the patient's medical history. New clinically significant findings after first dose must be included as AEs. Subsequent assessments beyond screening should be characterized as new, worsening, improved, or unchanged relative to the previous assessment.

#### **9.9.14. Adverse Event Collection**

Patients should be observed for general appearance, presence of illness or injury, or signs indicative of a concurrent illness at the times indicated in [Table 3](#), [Table 4](#), and [Table 5](#). Patients should be instructed to volunteer any information regarding AEs at any time during the study. The study physician or the study staff should also query patients with an open question regarding any AEs they may be experiencing (e.g., "How do you feel?" or "How have you been feeling since your last visit?"). Any findings are to be documented.

#### **9.9.15. Clinical Chemistry**

Blood samples will be collected for clinical chemistry analyses at the times indicated in [Table 3](#), [Table 4](#), and [Table 5](#). Clinical chemistry analyses are listed in [Table 6](#). Every effort should be made to collect laboratory data using the central lab. Where use of the central lab is not possible, laboratory assessments should be collected through a local lab and reviewed by the investigator. For calculation of the eGFR, the 4-variable MDRD equation must be used. The equation is as follows:

$$\text{eGFR} = 175 \times \text{standardized serum creatinine}^{-1.154} \times \text{age}^{-0.203} \times 1.212 \text{ [if black]} \times 0.742 \text{ [if female]}$$

**Table 6: Clinical Chemistry Assessments**

Clinical Chemistry Assessments
Blood urea nitrogen (BUN)
Creatinine
Total bilirubin (TBL)
Alanine aminotransferase (ALT)
Aspartate aminotransferase (AST)
Alkaline phosphatase (ALP)
Ferritin
Sodium
Potassium
Calcium
Inorganic phosphorus
Magnesium
Chloride
Bicarbonate
Uric acid
Cholesterol
Total protein
Glucose
Triglycerides
Albumin
Creatine phosphokinase (CPK)
Creatine kinase isozyme (only if CPK is > ULN)
Lactate dehydrogenase (LDH)
High-density lipoprotein cholesterol (HDL-C)
Low-density lipoprotein cholesterol (LDL-C)
Very-low-density lipoprotein cholesterol (VLDL-C)
Gamma-glutamyl transpeptidase (GGT)
Estimated glomerular filtration rate (eGFR) using the MDRD-4 formula

**9.9.16. Hematology**

Blood samples will be collected for hematology assessments at the times indicated in [Table 3](#), [Table 4](#), and [Table 5](#). Hematology assessments are listed in [Table 7](#). Every effort should be made to collect laboratory data using the central lab. Where use of the central lab is not possible, laboratory assessments should be collected through a local lab and reviewed by the investigator. As noted in [Table 7](#), HbA1c will only be collected at Screening and Week 12 visits.

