**Figure 1: Schema for Part 1 and Part 2 Evaluation of RTA 408 in Patients with Friedreich’s Ataxia**

**Extension:** The extension will assess long-term safety and tolerability of RTA 408 in qualified patients with Friedreich’s ataxia following completion of Part 1 or Part 2. Patients will not be unblinded to study treatment in Part 1 or Part 2 upon entering the extension study.

[figure not shown]
Patients will receive open-label RTA 408 (150 mg) once daily until the drug is available through commercial channels, or until patient withdrawal, whichever is sooner. All patients in the extension will follow the same visit and assessment schedule. Extension Day 1 is defined as the first day treatment is dispensed to the patient for the extension, following completion of Part 1 or Part 2. All other extension visits will be relative to extension Day 1. Patients will be scheduled for in-person assessments during treatment in the extension at Day 1, Weeks 4, 10, 16, and 24, and every 24 weeks thereafter. Patients will also be assessed by telephone contact on Day 14.

Since Part 2 patients will be followed continuously within the study, eligibility for the extension should be assessed at the Week 52 visit and a separate screening visit is not required. After confirming eligibility for Part 2 patients, study treatment for extension Day 1 should be dispensed following the Week 52 assessments. Part 1 patients will not have been followed continuously within this study, and therefore must complete a screening visit to confirm eligibility.

The conduct of the extension phase, according to protocol specifications, was impacted by the Coronavirus Disease 2019 (COVID-19) pandemic. As a result, and as of Version 10.1 of the Protocol, modifications intended to address access to and administration of investigational

product, and adherence to protocol-specified visits and laboratory assessments was implemented. These modifications are described in the [Appendix 13](#) (COVID-19 Mitigations).

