**Table 5: Extension Schedule of Assessments**

Study Day/Week	Screening a	Day 1 b	Week 2 (telephone)	Week 4	Week 10	Week 16	Week 24 + Every 24 Weeks	End of Study
Day Relative to First Dose in Extension	-30 to -1	1	14 (±3 days)	28 (±3 days)	70 (±3 days)	112 (±3 days)	168, 336, 504, etc. (±14 days)	Within 30 days after last dose
Informed consent	X							
Inclusion/Exclusion	X	X						
Pes cavus assessment	X							
Medical history	X							
Adverse event collection		X c	X	X	X	X	X	X
Prior and Concomitant medications	X	X	X	X	X	X	X	X
Weight and BMI	X	X d		X	X	X	X	X
Vital sign measurements	X	X d		X	X	X	X	X
Physical examination	X	X d		X	X	X	X	X
Height	X			X j				
Echocardiogram e	X							
Electrocardiogram e	X							
Clinical Chemistry	X			X	X	X	X	X
Hematology	X			X	X	X	X	X
Urinalysis and microscopy	X			X	X	X	X	X
BNP and NT-proBNP f	X			X	X	X	X	X
Hepatitis B and C and HIV 	X							
Pregnancy test WOCBP h	X	X		X	X	X	X	X
Dispense study drug		X		X			X	
Study drug return and pill count				X			X	X
Neurologic FARS		X					X	X
Activities of Daily Living		X					X	X
Patient Global Impression of Change							X	
Clinical Global Impression of Change							X	
25-foot Timed Walk Test		X					X	X
9-Hole Peg Test		X					X	X

Abbreviations: BMI=body mass index; BNP= B-type natriuretic peptide; FARS=Friedreich's ataxia rating scale; HIV=human immunodeficiency virus; NT-proBNP= N-terminal prohormone of B-type natriuretic peptide; WOCBP=women of childbearing potential.

a The screening visit is only required for Part 1 patients. Assessments collected at Part 2 - Week 48 or Part 2 - Week 52 should be used to assess eligibility for Part 2 patients.

b On Day 1, all required procedures should be performed and eligibility confirmed before study drug is dispensed in the extension.

c Adverse event assessments on Day 1 should be performed following study drug administration.

d For patients enrolled in Part 2 of the study, visit procedures required at Week 52 and also Extension Day 1 should only be performed once since Part 2 Week 52 and Extension Day 1 should occur on the same day.

e For patients with echocardiograms and electrocardiograms collected within 90 days prior to the Screening Visit, the most recent echocardiogram and electrocardiogram can be used to assess patient eligibility.

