### **8.3. Extension Eligibility**

Patients must complete 12 weeks of treatment in Part 1, or 48 weeks of treatment in Part 2, have no significant protocol deviations that would, in the opinion of the investigator, deem the patient unsuitable for enrollment in the Extension phase of the study, and continue to meet inclusion and exclusion criteria as specified in [Appendix 1](#).

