**Table 7: Hematology Assessments**

Hematology Assessments
Hematocrit
Hemoglobin
HbA1C (Screening, Week 12)
Red blood cell (RBC) count
White blood cell (WBC) count
Neutrophils
Bands (if detected)
Lymphocytes
Monocytes
Basophils (if detected)
Eosinophils (if detected)
Absolute platelet count
Mean corpuscular hemoglobin (MCH)
Mean corpuscular volume (MCV)
Mean corpuscular hemoglobin concentration (MCHC)
Reticulocyte count

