### Extension Exclusion Criteria

Patients must not:

1. Have uncontrolled diabetes (HbA1c > 11.0%)
2. Have B-type natriuretic peptide (BNP) level > 200 pg/mL
3. Have a history of clinically significant left-sided heart disease and/or clinically significant cardiac disease, with the exception of mild to moderate cardiomyopathy associated with Friedreich's ataxia, including but not limited to any of the following:
  - a. Clinically significant congenital or acquired valvular disease
  - b. Pericardial constriction (based on echocardiogram performed at Screening Visit or within 90 days prior to Screening Visit)
  - c. Restrictive or congestive cardiomyopathy (based on echocardiogram performed at Screening Visit or within 90 days prior to Screening Visit)
  - d. Symptomatic coronary disease (prior myocardial infarction, percutaneous coronary intervention, coronary artery bypass graft surgery, or angina)
  - e. History of hospitalization for heart failure in the last five years
  - f. Cardiac insufficiency, defined as New York Heart Association Class > 2

- g. History of atrial fibrillation
  - h. History of unstable arrhythmias
4. Have known active fungal, bacterial, and/or viral infection, including human immunodeficiency virus (HIV) or hepatitis virus (B or C)
  5. Have known or suspected active drug or alcohol abuse, as per investigator judgment
  6. Have clinically significant abnormalities of clinical hematology or biochemistry, including but not limited to elevations greater than 1.5 times the upper limit of normal of AST or ALT. Levels above this threshold are allowable if attributable to muscle injury
  7. Have any abnormal laboratory test value or clinically significant pre-existing medical condition that, in the opinion of the investigator, would put the patient at risk by study enrollment
  8. Have taken any of the following drugs within 7 days prior to Extension Day 1 or plan to take any of these drugs during the time of study participation:
    - a. Sensitive substrates for cytochrome P450 2C8 or 3A4 (e.g., repaglinide, midazolam, sildenafil)
    - b. Moderate or strong inhibitors or inducers of cytochrome P450 3A4 (e.g., carbamazepine, phenytoin, ciprofloxacin, grapefruit juice)
    - c. Substrates for p-glycoprotein transporter (e.g., ambrisentan, digoxin)

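### Part 2 patients have no scheduled HbA1c after Week 12, so the HbA1c exclusion for the extension is applied to a value 36 to 40 weeks old

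*Protocol*

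**What the plan says.** Section 9.9.16 covers hematology for all three schedules (Tables 3, 4 and 5) and states that "HbA1c will only be collected at Screening and Week 12 visits". Table 7 carries the same restriction: "HbA1C (Screening, Week 12".

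Section 8.3 requires patients entering the extension to "continue to meet inclusion and exclusion criteria as specified in" Appendix 1. The first exclusion there reads "Have uncontrolled diabetes (HbA1c > 11.0" percent.

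For patients coming from Part 2, Section 7.1 says that "eligibility for the extension should be assessed at the Week 52 visit and a separate screening visit is not required". Table 5 footnote a limits the extension screening visit to Part 1 patients and says that what was collected at Part 2 Week 48 or Week 52 "should be used to assess eligibility for Part 2 patients". Footnote b requires all Day 1 procedures to be done and "eligibility confirmed before study drug is dispensed in the extension". Footnote d tells sites not to repeat shared procedures, "since Part 2 Week 52 and Extension Day 1 should occur on the same day".

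**The concern.** The protocol sets a numeric safety exclusion, says which visits supply the data for it, and then schedules no measurement at those visits. Under Section 9.9.2 and Table 5 footnote b, the investigator must be satisfied that no exclusion applies before dispensing. For HbA1c the only scheduled post-baseline result comes from the first quarter of the treatment period.

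The timing looks like a carry-over from Part 1, although the protocol does not say so. In Part 1, Week 12 is the end of treatment. In Part 2 the end of treatment moved to Week 48, and the HbA1c timing did not move with it.

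What is at stake is safety screening for the extension. A patient whose diabetic control had worsened past the limit after Week 12 could enter open-label treatment without the stated exclusion being applied to a current value. The Part 2 endpoints, randomization, blinding and error control are not involved.

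**Working it through.** The protocol states no age for the HbA1c value, so there is no figure of its own to reproduce. The check is date arithmetic on the schedule and a comparison of the tables.

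**Inputs (Table 4).** Week 12 is Day 84, Week 48 is Day 336 and Week 52 is Day 364, each ±3 days.

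**Age of the latest scheduled HbA1c**
- At Week 48: 336 − 84 = 252 days; 252 / 7 = 36 weeks. With both windows: 252 ± 6 = 246 to 258 days.
- At Week 52: 364 − 84 = 280 days; 280 / 7 = 40 weeks. With both windows: 280 ± 6 = 274 to 286 days.

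**Share of treatment after that value.** 252 / 336 = 75% of the 48-week treatment period.

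**If the Week 12 sample was missed.** The Screening value (Day −60 to Day −1, no Day 0) is then the latest. On nominal visit days its age is 336 to 395 days (48 to 56.4 weeks) at Week 48 and 364 to 423 days (52 to 60.4 weeks) at Week 52.

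**Opportunities to measure.** Table 4 has hematology draws after Week 12 at Weeks 18, 24, 36, 48 and 52. That is five draws, none of which includes HbA1c under Section 9.9.16 and Table 7.

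**Comparison with the other numeric limits in Appendix 1**

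| Limit | Value at Part 2 Week 48 (Table 4)? |
|---|---|
| eGFR | Yes (chemistry) |
| Left ventricular ejection fraction | Yes (echocardiogram) |
| BNP | Yes |
| ALT/AST | Yes (chemistry) |
| Bilirubin | Yes (chemistry) |
| ALP | Yes (chemistry) |
| Albumin | Yes (chemistry) |
| HbA1c | No |

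Seven of the eight have a Week 48 value. HbA1c is the exception.

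**After entry.** Extension visits fall at Day 1, Weeks 4, 10, 16 and 24, and then every 24 weeks. None is a Week 12 visit, so the rule gives Part 2 patients no HbA1c in the extension either.

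**Time available for a result.** From a Week 48 draw to dispensing at Week 52: 364 − 336 = 28 days. Shortest: 361 − 339 = 22 days. Longest: 367 − 333 = 34 days. A Week 52 draw leaves no such interval, because Week 52 and Extension Day 1 are the same day.

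**The case against.** Four arguments can be made for the plan.

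1. **No recency limit is stated for HbA1c.** Where the protocol wants recent data it says so, for example 90 days for the echocardiogram. For hepatitis and HIV it accepts a negative titer from the past year. This is true of the exclusion itself. However, Section 8.3 requires that the criteria still be met, and Table 5 footnote a names Week 48 or Week 52 as the data source. Together these work as a recency rule that a Week 12 value does not satisfy.

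2. **Screening could be read to include its substitute.** Table 5 has a Screening column with hematology marked, and footnote a replaces that column with Week 48 or Week 52 for Part 2 patients. A site might therefore run HbA1c then. No text says so. Section 9.9.16 uses the word only, and footnote a refers to assessments already collected. If this was the intention, a clarifying line is still needed.

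3. **Other safeguards exist.** Part 2 patients met the same limit at study entry. Serum and urine glucose are measured at Weeks 18, 24, 36, 48 and 52. Section 9.6 allows unscheduled tests. Appendix 1 also excludes any abnormal laboratory value that the investigator considers a risk, and it requires a potentially favorable benefit-risk judgement. All of this stands and lowers the risk. None of it requires an HbA1c or lets glucose stand in for it.

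4. **Part 2 is over.** Appendix 13 says so, and any change needs an amendment under Section 17.5. This also stands. The gap at entry cannot be closed for patients already enrolled; only monitoring in the extension can still be improved.

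**Conclusion.** The concern holds and is minor. For Part 2 patients the prescribed source of eligibility data contains no HbA1c. The latest scheduled value is 36 weeks old at Week 48 and 40 weeks old at Week 52.

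The ages assume that visits took place within their windows and that the Week 12 sample was obtained. The conclusion also assumes that Screening in Section 9.9.16 and Table 7 means a screening visit and not the visits that replace it. Sites may have ordered HbA1c on their own initiative, and the documents do not show whether they did.

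At most about 100 patients (the planned Part 2 enrollment) are concerned. In practice there are fewer, because Appendix 1 excludes anyone who stopped treatment early. How many would have changed eligibility cannot be estimated, since the documents give no HbA1c data; the number is probably very small. Part 1 patients are not affected, because they have an extension screening visit with hematology.

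**What to change.** - **In the Part 2 schedule, and wherever this design is reused:** add HbA1c at Week 48 to Section 9.9.16 and Table 7, using the hematology sample already drawn there. The result then has 22 to 34 days to arrive before dispensing. Week 52 is a poorer choice, because the result may come back after drug has been handed out.
- **For patients already in the extension:** add one HbA1c to the next scheduled hematology draw in Table 5. This is safety monitoring and not a retrospective eligibility check. Section 8.5.1 has no HbA1c stopping rule, so the investigator would judge the result.

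The cost is one extra assay per patient on blood already being drawn, plus one line each in Section 9.9.16, Table 7 and Table 5. The edits need an amendment with the approvals in Section 17.5, so they are best included with the next amendment made for other reasons.
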